- e. Physical exam, hematology, biochemistry, and coagulation do not have to be repeated on Day 1 if performed within 48 hours as a screening/baseline assessment.
- f. Heart rate, diastolic and systolic blood pressure, respiratory rate, body temperature.
- g. 12-lead triplicate digital ECG will be performed with 2-minute intervals after at least 10 minutes rest in supine position. On Cycle 1 Day 1 and Day 15 at pre-dose and 1, 2, 4, 5, 6, 8, 12 hours and 24 hours post-dose (\pm 15 minutes) and on pre-dose on Day 8. The SMC may decide that the Day 15/Day 16 assessment can be waived in case no relevant drug accumulation is being observed. ECG assessments at subsequent cycles will be performed pre-dose at time points as indicated in the table. ECGs should be performed directly before PK sampling time points on days where both assessments are performed.
- h. Hemoglobin, white blood cell count, differential, platelet count, creatinine, creatinine clearance AST, ALT, GGT, AP, lipase, amylase, BUN, total bilirubin, total protein, albumin, uric acid, sodium, chloride, bicarbonate, potassium, calcium, phosphorus, magnesium and glucose, PT, aPTT and INR.
- i. Standard urine test, and pregnancy test will be done at each visit after Cycle 2 (corresponds to women of childbearing potential).

CCI

CCI

CCI

- m. PK time points: 3 mL (2 aliquots of 1.5 mL) blood each at following time points: QD dosing: Cycle 1 Day 1: 0 hour (pre-dose within 60 minutes prior to each treatment administration) and 1 (\pm 10 minutes), 2 (\pm 10 minutes), 3 (\pm 10 minutes), 4 (\pm 20 minutes), 5 (\pm 20 minutes), 6 (\pm 30 minutes), 8 (\pm 30 minutes), 12 hours post-dose (\pm 60 minutes), on Day 2 at 24 hours post-dose (before next drug administration) (\pm 60 minutes). Cycle 1 Day 8: 0 hour (pre-dose within 60 minutes prior to treatment administration), Cycle 1 Day 15: 0 hour (pre-dose within 60 minutes prior to each treatment administration) and 1 (\pm 10 minutes), 2 (\pm 10 minutes), 3 (\pm 10 minutes), 4 (\pm 20 minutes), 5 (\pm 20 minutes), 6 (\pm 30 minutes), 8 (\pm 30 minutes), 12 hours post-dose (\pm 120 minutes), on Day 16 at 24 hours post-dose (before next drug administration) (\pm 60 minutes), 63 mL blood in Cycle 1. Cycle \geq 2 Day 1: 0 hour (pre-dose within 60 minutes prior to each treatment administration).

CCI

CCI

- p. Pre-dose; optional blood sample: collection will only be performed after an Informed Consent Form has been signed.

CCI

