5.1.3.1 Part 1, M8891 Single Agent, Solid Tumors

The treatment period will begin at the first dose of M8891 in Cycle 1 Day 1 and consist of consecutive 21-day cycles of continuous once daily M8891 monotherapy under fasting conditions.

Subjects will receive M8891 at the pre-specified dose level until disease progression, unacceptable toxicity, withdrawal of consent, or any criterion for withdrawal from the study (Section 5.5.2).

If the subject tumor evaluation indicates that the disease is slowly progressing according to the CT scan as per Response Evaluation Criteria in Solid Tumors (RECIST) v1.1 criteria (a growth of the target lesions of less than 35% from baseline and no new lesions, or new lesion(s) smaller than 1 cm; bone metastatic lesions or lesions treatable with local radiotherapy would also fall in the same category), but the subject performance status is the same as baseline and there are no safety concerns, i.e. no ongoing symptomatic events Grade 2 or higher in severity, treatment may be continued for another 2 cycles to the next tumor evaluation, upon evaluation by the treating physician and after the continuation of therapy has been discussed with the Sponsor.

CCI

In principle, dose escalation of M8891 will proceed according to the decision of the SMC to the MTD, or the SMC may decide ceasing further dose escalation following review of safety, tolerability, PK and CC results.

The selection of the recommended dose for the expansion cohort of M8891 is based on the following criteria derived from the PK/C_{max} model:

CCI

The MS100015-0019 trial employs a Bayesian two-parameter logistic regression model with overdose control to assist the SMC with dose selection (Babb 1998; Neuenschwander 2008). The model incorporates nonclinical toxicity and observed DLT information from all previously completed dose escalation cohorts to provide a dose recommendation for the next dose cohort. The SMC will decide on the next dose level based on the Bayesian model, safety, PK analyses CCI [REDACTED] Dose escalation will start at 7 mg administered once daily.

A preselected set of doses (8 projected escalation steps with doses of 7, 12, 20, 35, 60, 100, 150 and 210 mg QD) are considered by the model, although doses may be skipped and/or others that are not part of the pre-specified set may be chosen as well. Sequential cohorts of 3 subjects at the same dose level will be used.

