- AUC_{0-t} : Area under the concentration-time curve from time zero to the last sampling time at which the concentration is at or above the lower limit of quantification (LLOQ)
- $AUC_{0-\tau}$: Area under the plasma concentration versus time curve within one dosing interval
- $t_{1/2}$: Apparent terminal half-life
- λ_z : Apparent terminal rate constant
- CL/F : Apparent body clearance of drug following extravascular administration
- CL_{ss}/F : Apparent body clearance of drug following extravascular administration at steady state
- V_z/F : Apparent volume of distribution during the terminal phase following extravascular administration
- $Racc(AUC_\tau)$: Accumulation ratio for AUC_τ
- $Racc(C_{max})$: Accumulation ratio for C_{max} .

In dose level 4 and dose level 5, urine samples for exploratory determination of M8891 and its metabolites will be taken from the total pooled urine sample provided during the 12-hour collection period on Day 1 and Day 15. The start and stop date/time of each pooled urine collection should be recorded in the eCRF. The volume of each urine collection will also be recorded.

Additional analyses may be conducted on the plasma and/or urine samples to further investigate the presence and/or identity of drug metabolites. Any results from such analyses on plasma and/or urine may be reported separately from the clinical trial report.

Details on sample shipment and handling will be provided in the Laboratory Manual.

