AUCτ	The area under the concentration-time curve (AUC) over the dosing interval from T_1 =0 h to T_2 = τ h. Calculated using the mixed log linear trapezoidal rule (linear up, log down). For single dose, AUC τ is calculated as a partial area with the defined time range. In multiple dose profiles AUC τ is calculated at steady state from one pre-dose time point to the dosing interval time. In cases where the actual observation time is not equal to the scheduled observation time AUC τ will be calculated based on the estimated concentration at τ hours, and not the concentration at the actual observation time.
AUC _τ /Dose	The Dose normalized AUC over the interval from T_1 =0 h to T_2 = τ h. Normalized using actual dose, using the formula $AUC_{\tau}/Dose$.
AUCextra%	The AUC from time t_{last} extrapolated to infinity given as percentage of $AUC_{0-\infty}$. $AUC_{extra\%} = (extrapolated area/AUC_{0-\infty})*100 = (1 - [AUC_{0-t}/AUC_{0-\infty}])*100$.
λ_z	Terminal first order (elimination) rate constant. Determined from the terminal slope of the log-transformed concentration curve using linear regression on terminal data points of the curve
t _{1/2}	Apparent terminal half-life. $t_{1/2} = \ln (2)/\lambda_z$
CL/f	The apparent total body clearance of drug following extravascular administration, taking into account the fraction of dose absorbed. $CL/f = Dose_{p.o.}/AUC_{0-\infty}$.
CL _{SS/f}	The apparent total body clearance of drug at steady state following extravascular administration, taking into account the fraction of dose absorbed. $CL_{SS/f} = Dose_{p.o.} / AUC_{\tau}$
CLR	The renal clearance of drug. $CL_R = Ae_{0-\infty}/AUC_{0-\infty}$ or Ae_{0-t}/AUC_{0-t}
$V_{\mathrm{Z/f}}$	The apparent volume of distribution during the terminal phase following extravascular administration, based on the fraction of dose absorbed. $V_{z/f} = Dose/(AUC_{0-\infty}*\lambda_z)$ following single dose. $V_{z/f} = Dose/(AUC_{\tau}*\lambda_z)$ following multiple dose.
Racc(AUC)	The accumulation factor to assess the increase in exposure until steady state is reached. $R_{acc(AUC)}=(AUC_{\tau} \text{ after multiple dose (at steady state)}) / (AUC_{0-\infty} \text{ after single dose})$

R _{acc(Cmax)}	The accumulation factor to assess the increase in maximum concentration until steady state is reached. $R_{acc(Cmax)} = (C_{max} \text{ after multiple dose (at steady)})$

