	steady state is reached. $R_{acc(Cmax)} - (C_{max} \text{ after multiple dose (at steady state)})/(C_{max} \text{ after single dose}) = C_{max} D_{15}/C_{max} D_{1}$

The following urine PK parameters of M8891 will be calculated, when reliable, for the QD and BID dosing, on Day 1 and Day 15:

Ae_{τ}	The cumulative amount excreted during a complete dose interval at steady state. Amount_Recovered = Σ (Concentration * Volume) from T_1 to T_2 , where T_1 and T_2 denote the start and end time of the dose interval at steady state respectively.
Aeτ%	The cumulative percentage of dose excreted during a complete dose interval at steady state. Percent_Recovered = 100*Amount_Recovered/Dose.
Ae _{0-t}	The cumulative amount excreted from time zero (= dosing time) to the end of the current collection interval after dosing. Amount_Recovered = Σ (Concentration * Volume)
Ae _{0-t} %	The cumulative percentage of dose excreted from time zero (= dosing time) to the end of the current collection interval after dosing. Percent_Recovered = 100*Amount_Recovered/Dose
Ae _{0-∞}	The cumulative amount excreted from time zero (dosing time) to infinity. $ Ae_{0-\infty} = Ae_{0-t} + ((Ae_{0-(t-1)} - Ae_{0-t})/(t_{last-1} - t_{last}))/\lambda_z \text{ where } \lambda_z \text{ is the excretion rate or } Ae_{0-\infty} = (Ae_{0-t} / AUC_{0-t}) * AUC_{0-\infty} $
Ae _{0-∞} %	The cumulative percentage of the dose that is excreted from time zero (= dosing time) to infinity. Percent_Recovered = 100*Amount_Recovered/Dose

The following PK parameters will be calculated for diagnostic purposes and listed, but will not be summarized:

- The time interval (h) of the log-linear regression ($\lambda_{z \text{ low}}$, $\lambda_{z \text{ upp}}$) to determine λ_{z} .
- Number of data points (N_{λ}) included in the log-linear regression analysis to determine λ_z .
- Goodness of fit statistic (Rsq) for calculation of λ_z .

The regression analysis should contain data from at least 3 different time points in the terminal phase consistent with the assessment of a straight line on the log-transformed scale. Phoenix WinNonlin best fit methodology will be used as standard. The last quantifiable concentration

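### In SAP 16.1.2 the urine amount stops at 12 h while the plasma area can run to 24 h, so under once-daily dosing CLR from Ae0-t/AUC0-t is biased low and Ae-tau is not observed

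*SAP*

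**What the plan says.** **Urine.** Protocol 7.5.1 limits urine PK to two dose levels and calls it exploratory: "In dose level 4 and dose level 5, urine samples for exploratory determination of M8891 and its metabolites". The material is the "total pooled urine sample provided during the 12-hour collection period on Day 1 and Day 15". No collection from 12 to 24 h is described. SAP 16.1.1 sums the voids within a collection.

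**Dosing and plasma.** Part 1 is given as "consecutive 21-day cycles of continuous once daily M8891 monotherapy under fasting conditions" (Protocol 5.1.3.1), so tau is 24 h. Protocol Table 1, footnote m, schedules plasma samples to 12 h and then "on Day 2 at 24 hours post-dose (before next drug administration"), with the same pattern after Day 15: "on Day 16 at 24 hours post-dose (before next drug administration").

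**SAP 16.1.2 definitions.**
- CLR ("The renal clearance of drug") is Ae0-infinity/AUC0-infinity or Ae0-t/AUC0-t.
- In Ae0-t, t is the close of the urine collection. In AUC0-t, t is the last quantifiable plasma sample.
- Ae-tau is "The cumulative amount excreted during a complete dose interval at steady state".
- Ae0-infinity has two routes. One extrapolates from the excretion rate between the last two collection times. The other multiplies Ae0-t/AUC0-t by AUC0-infinity.
- The urine parameters "will be calculated, when reliable, for the QD and BID dosing, on Day 1 and Day 15".

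**The concern.** A renal clearance is an amount excreted divided by the plasma area over the same time. Here the numerator stops at 12 h, while the denominator continues for as long as plasma stays quantifiable, possibly to 24 h. Someone programming the two definitions literally would divide a 12 h amount by an area of up to 24 h.

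Ae-tau and its percentage of dose have a related problem. Under once-daily dosing the second half of the interval is never collected, and the SAP gives no rule for filling it.

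Both errors are systematic, so adding subjects does not reduce them. What is at stake is a reported renal clearance and fraction excreted for a first-in-human drug that could be well below the true values.

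**Working it through.** The documents give no figure for CLR, Ae or half-life to reproduce. One check on the plasma schedule is possible. Ten samples on Days 1/2, one on Day 8 and ten on Days 15/16, at 3 mL each, give (10 + 1 + 10) x 3 = 63 mL. That is the Cycle 1 volume in Table 1, footnote m, so the 24 h sample belongs to both profiles.

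**Assumptions (not in the documents).** One compartment, linear kinetics, constant renal clearance, complete urine collection, and plasma quantifiable to 24 h. Half-life is varied from 3 to 48 h. Absorption is instantaneous or slow (ka 0.3 per h). Then Ae0-12 = CLR x AUC0-12, and k = ln 2 / half-life.

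**1. CLR as Ae0-t/AUC0-t.** The value relative to truth is AUC0-12/AUC0-24. With instantaneous absorption this is (1 - exp(-12k)) / (1 - exp(-24k)) = 1/(1 + exp(-12k)). At a 6 h half-life, exp(-12k) = 0.25, so the ratio is 1/1.25 = 0.80.

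**2. Ae-tau under once-daily dosing, from 12 h of urine.** The relative value is AUC0-12/AUC0-24 at steady state. With instantaneous absorption the formula is the same as in step 1.

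| Half-life | CLR Day 1 and Ae-tau, instantaneous | CLR Day 1, ka 0.3 | Ae-tau, ka 0.3 |
|---|---|---|---|
| 3 h | 0.94 | 0.83 | 0.83 |
| 6 h | 0.80 | 0.68 | 0.69 |
| 12 h | 0.67 | 0.56 | 0.59 |
| 24 h | 0.59 | 0.49 | 0.54 |
| 48 h | 0.54 | 0.46 | 0.52 |

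**3. Ae0-infinity by scaling.** CLR = [(Ae0-t/AUC0-t) x AUC0-infinity] / AUC0-infinity = Ae0-t/AUC0-t. The bias is that of step 1.

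**4. Ae0-infinity by excretion rate.** The formula needs Ae at two successive collection times, and one pooled sample supplies one. If the earlier point were set to zero, CLR relative to truth would be (Ae0-12 + (Ae0-12/12)/lambda_z)/AUC0-infinity. With instantaneous absorption that is 1.28, 1.29, 1.22, 1.14 and 1.08 at half-lives of 3, 6, 12, 24 and 48 h. With ka 0.3 it runs from 1.12 down to 0.80. The direction is not fixed.

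**5. Matched windows.** Ae0-12/AUC0-12 = CLR x AUC0-12/AUC0-12 = CLR. The relative value is 1.00 at every half-life and absorption rate.

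**The case against.** Several points limit the concern.

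- **Intent.** The SAP calls for standard non-compartmental methods, and a shared subscript could be read as a shared interval. That is probably what a pharmacokineticist would do. But each t has its own explicit definition, and the two differ.
- **The reliability qualifier.** It might keep the affected parameters out of the report. However, the stated criteria concern the terminal slope and the AUC extrapolation. None addresses incomplete urine, and values failing them are flagged and still summarised.
- **Ae0-12 is already there.** This stands. With a 12 h collection, the SAP's Ae0-t and its percentage of dose are the 12 h quantities. Only the label is missing.
- **Twice-daily dosing.** Under BID, which the SAP still covers, 12 h is a complete interval and Ae-tau is fully observed. The current protocol lists Part 1 PK after once-daily dosing only, so the Ae-tau point holds for that schedule.
- **Size.** The bias can be small. At a 2 h half-life with instantaneous absorption the ratio is 1/(1 + 1/64) = 0.98. If the last quantifiable plasma sample falls at or before 12 h, the CLR mismatch shrinks or vanishes.
- **Versions and redaction.** The SAP is version 1.0 and refers to protocol version 2.0, which is not available. The Table 1 footnote for urine PK is blacked out. The 12 h window therefore rests on Section 7.5.1 of the current protocol.

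A reader might infer that the SAP defines CLR over 24 h, or that every permitted route biases it low. Neither follows: CLR is given through two differing meanings of t, and the excretion-rate route is undefined or can err either way. A reader might also infer that these values drive renal dosing or eligibility decisions. No section says so.

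**Conclusion.** The mismatch is real as written. Under once-daily dosing, Ae0-t/AUC0-t and the Ae0-infinity route that scales it understate renal clearance whenever plasma is quantifiable beyond 12 h. Ae-tau cannot be observed, and is low if filled with the 12 h amount.

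Under the assumed model and half-lives of 3 to 48 h, CLR is 6% to 46% low with instantaneous absorption and 17% to 54% low with slow absorption. Ae-tau is 6% to 46% and 17% to 48% low. These are ranges under assumption, not estimates for M8891. Linear kinetics is itself assumed, and Protocol 3.3.1 reports a less than proportional exposure increase at 60 mg. The direction of the bias in the ratio does not depend on the model: with constant renal clearance, any quantifiable plasma area after 12 h enlarges the denominator alone.

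The consequence is modest. Urine PK is exploratory, is limited to dose levels 4 and 5, and is absent from the protocol's endpoint and PK parameter lists. No primary or secondary conclusion depends on it.

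**What to change.** Amend SAP 16.1.2 as follows.

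1. Define CLR = Ae0-12/AUC0-12, with both terms over the actual urine collection window. Start and stop times are already recorded. The 12 h plasma sample exists on Days 1 and 15, and the SAP's partial-area rules allow interpolation to the recorded stop time. That matters on Day 15, when the 12 h plasma sample may be up to 120 minutes off schedule.
2. Label the existing Ae0-t and its percentage of dose as Ae0-12.
3. For once-daily dosing, either do not report Ae-tau and Ae0-infinity, or derive them as (Ae0-12/AUC0-12) x AUC-tau and (Ae0-12/AUC0-12) x AUC0-infinity and label them as extrapolated.
4. Remove the excretion-rate route to Ae0-infinity, which a single pooled collection cannot support.

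The cost is SAP wording and the matching programming. No new samples or visits are needed.

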16.1.3 Analysis of PK Parameters

All PK parameters will be listed using the safety population. Subjects that are not included in the PK analysis set will be flagged, and the list will be sorted so that they are at the bottom of the list.

The PK parameters will also be summarized descriptively per day by dose group using the PK analysis set.

The following tables and figures will be provided:

Tables

Individual Pharmacokinetic Parameters of M8891 in Plasma and Descriptive Statistics by Treatment after Single Dosing (Cycle 1 Day 1)

Individual Pharmacokinetic Parameters of M8891 in Plasma and Descriptive Statistics by Treatment after Multiple Dosing (Cycle 1 Day 15)

Individual Accumulation Ratios of AUC, Ae and Cmax in Plasma and Descriptive Statistics by Treatment

Individual Dose Normalized Pharmacokinetic Parameters of M8891 in Plasma and Descriptive Statistics after Single Dosing (Cycle 1 Day 1)

Individual Dose Normalized Pharmacokinetic Parameters of M8891 in Plasma and Descriptive Statistics after Multiple Dosing (Cycle 1 Day 15)

Figures

Scatter Plots: M8891 Dose-normalized PK Parameter (eg, AUC0-t, AUC0-∞ and Cmax) versus Treatment, Single Dose (with linear regression)

Box Plots: M8891 Dose-normalized PK Parameter (eg, AUC0-t, AUC0-∞-, and Cmax) versus Treatment, Single Dose

Scatter Plots: M8891 Dose-normalized PK Parameter (eg, AUC, and Cmax) versus Treatment, Multiple Dose (with linear regression)

Box Plots: M8891 Dose-normalized PK Parameter (eg, AUC, and Cmax) versus dose

16.1.4 Analysis of Dose Proportionality

For the assessment of dose proportionality, the PK endpoints, $AUC_{0-\tau}$, $AUC_{0-\tau}$, $AUC_{0-\tau}$ and C_{max} of M8891 will be compared between dose levels for Day 1 and Day 15 separately.

The PK parameters will be dose normalized

The dose normalized parameters and the overall mean (y-axis) will be plotted over the dose (x-axis) on the linear scale and logarithmic (both axes) scale using the PK analysis set. The overall mean will be calculated on the scale that is used for the plot.

Modeling on the log transformed scale will be applied to the dose normalized parameters including dose as covariate. Dose proportionality will also be checked using the power model, if appropriate. The relationship between the PK parameter y and the actual total dose is defined as follows:

$$y = \alpha dose^{\beta}$$

On the log transformed scale this becomes a linear relationship to which a linear regression approach can be applied:

$$log(y) = log(\alpha) + \beta * log(dose)$$

[figure not shown]
The estimate of β and 95% confidence intervals will be computed to quantify dose proportionality. If dose proportionality is given, β in theory is equal to 1 and the estimate of the model should not deviate strongly from 1. This linear regression will be calculated using the PK analysis set.

[figure not shown]
The SAS code for this analysis can be found in the TLF shells.

16.1.5 Population Pharmacokinetic Analysis

The PK and covariate data from this study may be analyzed jointly with data from other studies by nonlinear mixed effect approach, in order to describe the PK concentration time profile; to identify covariates explaining (part of) the between subject PK variability; and to estimate the residual PK variability. No standalone PopPK analysis on this trial is planned. For a combined PopPK analysis with other studies, more details will be given in a separate Data Analysis Plan for Population Pharmacokinetic Analysis. The results will be reported separately.

17 References

18 Appendices

18.1 Important Protocol Deviations

PD REF ID	Category (DVCAT)	Classification (DVDECOD)	Type of Deviation Observable/ Programmable (Data Driven)	PD (DVTERM	PD Identification Method Options	cIPD ?
100 CC	Important	Informed Consent	Observable	Subject has study-specific assessment performed prior to informed consent.	Source Data Review	
COI						
				Improper Informed Consent - Subject was not consented properly prior to screening procedures commencing		
102	Important	Informed Consent	Observable	(No consent, missing date, incorrect name)	Source Data Review	
200	Important	Inc/Excl Criteria	Observable	Subject does not have Histologically confirmed advanced solid tumors with no clear curative treatment options available after at least 1 prior systemic anticancer therapy, however subject is included in the trial.	Source Data Review	
201	Important	Inc/Excl Criteria	Observable	Missing tumor accessible for biopsies and agreement to conduct pre-dose and post-dose fresh tumor biopsies, however subject is included in the trial.	Source Data Review	
202	Important	Inc/Excl Criteria	Observable	Bone marrow impairment as evidenced by hemoglobin < 9.0 g/dL, neutrophil count < 1.5 x 109/L, platelets < 100 x 109/L. Transfusion is not allowed within 3 weeks before first dose, however subject is included in the trial.	Source Data Review	Yes

PD REF ID	Category (DVCAT)	Classification (DVDECOD)	Type of Deviation Observable/ Programmable (Data Driven)	PD (DVTERM	PD Identification Method Options	cIPD ?
000		Inc/Excl	2 1	Renal impairment as evidenced by calculated creatinine clearance < 60 mL/min (according to the Cockcroft-Gault formula), however subject is	Source Data	V
203	Important	Criteria	Observable	included in the trial.	Review	Yes
204	Important	Inc/Excl Criteria	Observable	Liver function abnormality as defined by total bilirubin > 1.5 x ULN, or AST/ALT > 2.5 x ULN, for subjects with liver involvement AST/ALT > 5 x ULN, however subject is included in the trial.	Source Data Review	Yes
205	Important	Inc/Excl Criteria	Observable	Extensive prior radiotherapy to more than 30% of bone marrow reserves, or prior bone marrow/stem cell transplantation within 5 years of study start, however subject is included in the trial.	Source Data Review	Yes
206	Important	Inc/Excl Criteria	Observable	Clinically significant cardiac conduction abnormalities, including QTc prolongation of > 480 msec and/or pacemaker or impaired cardiovascular function such as New York Heart Association classification score > 2, however subject is included in the trial.	Source Data Review	Yes
		Inc/Excl		Any other severe clinical condition that in the opinion of the treating physician may compromise the trial participation, however subject is included in the	Source Data	
207	Important	Inc/Excl Criteria	Observable Observable	trial. Participation in another clinical trial within the past 28 days, however subject is included in the trial.	Source Data Review	Yes

PD REF ID	Category (DVCAT)	Classification (DVDECOD)	Type of Deviation Observable/ Programmable (Data Driven)	PD (DVTERM	PD Identification Method Options	cIPD ?
				History of difficulty swallowing, malabsorption, or other chronic gastrointestinal disease or conditions that may hamper compliance and/or absorption of the		
209	Important	Inc/Excl Criteria	Observable	investigational drugs, however subject is included in the trial.	Source Data Review	
210	Important	Inc/Excl Criteria	Observable	Life expectancy < 3 months, however subject is included in the trial.	Source Data Review	
211	Important	Inc/Excl Criteria	Observable	Known hypersensitivity to the trial treatment or to one or more of the excipients used, however subject is included in the trial.	Source Data Review	
212	Important	Inc/Excl Criteria	Observable	Legal incapacity or limited legal capacity, however subject is included in the trial.	Source Data Review	
213	Important	Inc/Excl Criteria	Observable	The subject is a female of childbearing potential who is pregnant, breastfeeding or who did not agree to use effective contraceptive measures from time of informed consent through 92 days after last dose of study drug.	Source Data Review	
214	Important	Inc/Excl Criteria	Observable	The subject is male with partners of childbearing potential that did not use barrier contraception and did not have their partners use another method of contraception from the time of informed consent through 92 days after last dose of study drug.	Source Data Review	
215		Inc/Excl Criteria	Programmable	Eastern Cooperative Oncology Group Performance Status (ECOG PS) is not <2 however subject is included in study	On-Line Check	

PD REF ID	Category (DVCAT)	Classification (DVDECOD)	Type of Deviation Observable/ Programmable (Data Driven)	PD (DVTERM	PD Identification Method Options	cIPD ?
216	Important	Inc/Excl Criteria	Observable	History of stroke, heart attack, thrombosis (e.g. deep vein thrombosis and pulmonary embolism) or genetically-determined hypercoagulopathy within 6 months	Source Data Review	
217	Important	Inc/Excl Criteria	Observable	Patient did not receive at least 1 prior systemic anticancer therapy prior to enrolling in study.	Source Data Review	
218	Important	Inc/Excl Criteria	Observable	Subject received blood product transfusion 3 weeks prior to first dose of M8891.	Source Data Review	
222	Important	Visit Schedule	Programmable	Any abnormal complete neurologic examination test detected during treatment but Mini Mental Exam not done.	On-Line Check	
223	Immortant	Visit Cabadula	Dragramahla	Any abnormal complete neurologic examination test during treatment but International Cooperative Group for Ataxia Rating	On-Line	
300	Important	Visit Schedule Withdrawal Criteria	Programmable Observable	Scale (ICARS) not done. Patient met withdrawal criteria during the study but is still on study	Source Data Review	
301	Important	Withdrawal Criteria	Observable	Subject withdrew consent, and was not withdrawn from the trial therapy.	Source Data Review	

PD REF ID	Category (DVCAT)	Classification (DVDECOD)	Type of Deviation Observable/ Programmable (Data Driven)	PD (DVTERM	PD Identification Method Options	cIPD ?
302	Important	Withdrawal Criteria	Observable	Progressive neoplastic disease per RECIST v1.1 and the exceptions in protocol, a growth of the target lesions of less than 35% from baseline and no new lesions, or new lesion(s) smaller than 1 cm; bone metastatic lesions or lesions treatable with local radiotherapy would also fall in the same category), but the subject performance status is the same as baseline and there are no safety concerns, i.e. no ongoing symptomatic events Grade 2 or higher in severity, treatment may be continued for another 2 cycles to the next tumor evaluation, are not fulfilled but patient still on study	Source Data Review	
303		Withdrawal Criteria	Observable	Subject requires more than 2 dose reductions but is still on study	Source Data Review	
304		Withdrawal Criteria	Observable	Patient with treatment- emergent AE attributable to study drug and judged as clinical significance and deemed necessary to reduce the dose as per protocol but continued on study therapy at same dose administered when treatment-emergent AE occurred Patient with evidence of	Source Data Review	
305	Important	Withdrawal Criteria	Observable	treatment related hepatocellular injury but continued on study therapy at same dose administered when DLT occurred.	Source Data Review	

			Type of			
PD REF ID	Category (DVCAT)	Classification (DVDECOD)	Type of Deviation Observable/ Programmable (Data Driven)	PD (DVTERM	PD Identification Method Options	cIPD ?
				Patient with any Grade 4 liver enzyme elevation tha tis possibly drug related but continued on study therapy at same dose		
306	Important	Withdrawal Criteria	Observable	administered when DLT occurred.	Source Data Review	
				Patient with Grade 4 neutropenia lasting >5 days or Grade ≥3 neutropenia with fever but continued on study therapy at same dose		
307	laan antant	Withdrawal	Ohaamiahla	administered when DLT	Source Data	
307	Important	Criteria	Observable	occurred. Patient with Grade 4 thrombocytopenia lasting >5 days or Grade ≥3 thrombocytopenia with bleeding but continued on study therapy at same	Review	
308	Important	Withdrawal Criteria	Observable	dose administered when DLT occurred.	Source Data Review	
309	Important	Withdrawal Criteria	Observable	Patient with any treatment interruption >7 days or >30% of total dose in Cycle 1 due to Aes not related to the underlying disease or concomitant medication but continued on study therapy at same dose administered when DLT occurred.	Source Data Review	
		Withdrawal		Patient with any Grade ≥3 non-hematologic toxicity (excluding Grade 3 nausea or vomiting that lasts <48 hours, Grade 3 fatigue <5 days, Grade 3 HTN in the absence of maximal medical therapy, Grade 3 rash <5 days, Grade 3 electrolyte abnormality that lasts <72 hours and is not clinically complicated) but continued on study therapy at same dose administered when DLT	Source Data	
310	Important	Criteria	Observable	occurred.	Review	

PD REF ID	Category (DVCAT)	Classification (DVDECOD)	Type of Deviation Observable/ Programmable (Data Driven)	PD (DVTERM	PD Identification Method Options	cIPD ?
311	Important	Withdrawal Criteria	Observable	Discontinuation of M8891 is desired or considered necessary by the Investigator and/or the subject (if applicable) due to occurrence of > Grade 2 AEs for more than 6 days but subject not withdrawn from M8891 treatment	Source Data Review	
312	Important	Withdrawal Criteria	Observable	Subject experienced a DLT and was not withdrawn from the trial therapy.	Source Data Review	
313		Withdrawal Criteria	Programmable	Occurrence of pregnancy but subject was not removed from the trial therapy	Off-Line Manual Listing	
400	Important	AE/SAE	Observable	Safety Reports (SAE, IND) not reported to IRB as required. Safety Reports (SAE,	Source Data Review	
401	Important	AE/SAE	Observable	IND) not reported to EMD-GPS within 24 hours of event.	Source Data Review	
402	Important	AE/SAE	Observable	Pregnancies considered by the Investigator to be related to trial treatment resulting from a drug interaction with a contraceptive medication are not reported as an AEs.	Source Data Review	
500	Important	Visit Schedule	Programmable	Missing data for Physical Examination.	On-Line Check Off-Line Manual Listing	
501	Important	Visit Schedule	Programmable	Missing data for Vital signs.	Off-Line Manual Listing	
503	Important	Visit Schedule	Programmable	Missing data for pregnancy testing for Female subjects of Childbearing potential. Missing data for	On-Line Check	
505	Important	Visit Schedule	Programmable	Pharmacokinetic Blood sampling.	On-Line Check	Yes
531	Important	Visit Schedule	Programmable	ECG assessment is missing for "/timepoint/, /record #/".	Off-Line Manual Listing	

PD REF ID	Category (DVCAT)	Classification (DVDECOD)	Type of Deviation Observable/ Programmable (Data Driven)	PD (DVTERM	PD Identification Method Options	cIPD ?
554	Important	Visit Schedule	Observable	A minimum of 7 days laps not achieved between dosing of subject 1 and subsequent subject in each cohort without SMC approval.	Source Data Review	
547	Important	Visit Schedule	Observable	Screening assessment dates are not within 28 Days prior to informed consent for a subject that has been re-screened.	Source Data Review	
600	Important	IP Admin/Study Treat	Observable	Subject received / has taken wrong dose / treatment schedule of M8891 different from the planned for the subject.	Source Data Review	
601	Important	IP Admin/Study Treat	Observable	Noncompliance that is deemed by the Investigator or the Sponsor to compromise the patient's safety or trial integrity" but subject was not withdrawn	Source Data Review	
548	Important	Visit Schedule	Programmable	Missing data for safety (hematology, biochemistry, coagulation).	Off-Line Manual Listing	
700	Important	Disallowed Medications	Observable	Subjects taken potent combined inhibitors of CYP3A4, CYP2C9 and CYP2C19 (i.e. fluconazole and voriconazole) during treatment of M8891.	Source Data Review	Yes
549	Important	Visit Schedule	Programmable	End of Treatment Visit not performed.	Off-Line Manual Listing	
604	Important	IP Admin/Study Treat	Programmable	>4 missed administration in Cycle 1 and subject did not have a DLT Subjects is not refractory	Off-Line Manual Listing	Yes
219	Important	Inc/Excl Criteria	Observable	to or intolerant of existing cancer therapy(ies) known to provide clinical benefit	Source Data Review	

PD REF ID	Category (DVCAT)	Classification (DVDECOD)	Type of Deviation Observable/ Programmable (Data Driven)	PD (DVTERM	PD Identification Method Options	cIPD ?
220	Important	Inc/Excl Criteria	Observable	Protocol version 1.0: Presence of deep vein thrombosis based on screening lower extremity Doppler ultrasonography, or elevated D-dimer (> 0.5µg/mL) but subject enrolled in the study.	Source Data Review	
224	Important	Inc/Excl Criteria	Observable	Protocol version 2.0: Presence of deep vein thrombosis based on screening lower extremity Doppler ultrasonography but subject enrolled in the study.	Source Data Review	
221	Important	Inc/Excl Criteria	Observable	Missing data for complete neurologic examination	Source Data Review	
553	Important	Visit Schedule	Observable	A whole visit at the site is not performed	Source Data Review	

Integrated Analysis Plan for end of monotherapy dose escalation - Main Text Body

ELECTRONIC SIGNATURES

Signed by	Meaning of Signature	Server Date (dd-MMM-yyyy HH:mm 'GMT'Z)
PPD	Business Approval	PPD
PPD	Technical Approval	PPD
PPD	Technical Approval	PPD
PPD	Technical Approval	PPD
